Muscle and adipose are key metabolic tissues that undergo significant age-related changes, and play an active role in the pathogenesis of aging. ²⁷⁻²⁹ We are characterizing transcriptional changes with aging in these tissues, and studying the effects of therapeutic interventions. RNA-Seq analysis is being used to identify pathways targeted by candidate anti-aging drugs that have been tested in animals. In addition, we are accumulating a repository of muscle and adipose biopsy samples obtained from young healthy controls to establish a unique biological "fingerprint" for aging in these tissues by comparing changes in gene expression in older adults, post-drug therapy to the profiles of young healthy subjects. This overall approach is supported by a grant from the Glenn Foundation for the Study of the Biology of Human Aging and we are currently analyzing data from two prior studies using metformin and resveratrol. We have gene transcription profiles from RNA seq performed on fat and muscle biopsies from 4 young individuals and plan to recruit up to 30 more young participants under a separate protocol.

As part of our secondary analyses, we also plan to assess changes in microRNA levels in the serum. MicroRNAs (miRNAs) are small, non-coding RNAs that regulate gene expression at a post-transcriptional level. Due to their stability in blood, changes in expression of circulating miRNA might serve as markers for age-related pathologies. Investigators at Einstein have profiled B-lymphocyte miRNA levels in the plasma and have identified microRNA profiles associated with exceptional longevity. We hypothesize that acarbose treatment will alter the expression of circulating miRNAs in a way that may offer insight into anti-aging mechanisms of acarbose. Given the known effects of acarbose on colonic fermentation and composition of gut microbiota we plan to explore changes in gut microbiome using 16s rDNA seq. We plan to correlate changes in transcription (muscle and fat RNAseq), post-translational regulation (miRNA) and gut microbiome with changes in clinical metabolic outcomes and inflammatory biomarkers.

C. Research Methods:

C.1. Study Design & Protocol Summary: We propose a 22-week randomized, double-blind, placebo controlled cross-over study of acarbose in older adults (n=30) with impaired glucose tolerance.

		Treat-			Wash	Treat-		
		ment A			-out	ment b		
	Visit 1	Visit 2 0	Visit 3 4 wks	Visit 4 10 wks	2 wks	Phone call: 12wks	Visit 5 16 wks	Visit 6 22 wks

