these specifically implement a splice-junction aware alignment protocol. Pair-wise correlation and principal component analyses on each sample's gene expression profile will be used to determine the quality of the experiment, identify batch effects and other systematics. Differential expression between samples (young and old, and after acarbose and after placebo) will be determined, using a negative binomial model approach such as that implemented in the DESeq package. Genes that show an adjusted p-value of less than 0.05 and a fold change greater than 2 will be selected for further scrutiny between placebo and acarbose conditions. Furthermore, our RNA-seq data will permit us to identify splice variants between the experimental conditions. The differential gene list will be processed with Ingenuity Pathway Analysis and GoStat, allowing us to identify dysregulated pathways and common gene ontology terms differentiating the acarbose transcriptome for the tissue types under scrutiny. Finally, the entire differential expression profile will be processed using the Broad's Gene Set Enrichment Analysis platform against over 10,000 curated gene lists, to provide additional regulatory perspectives on the data. These analyses are considered exploratory in nature and will be used to inform future tests that may target specific gene expression pathways. It will also allow us to make collaborative associations with phenotypes, although these associations will be complex considering the numerous potential age-delaying effects that may occur, some of which may be independent of the measured physiologic parameters.

Insulin sensitivity, biomarkers, etc.: Differences in mean acarbose vs. placebo treatment outcomes (insulin sensitivity, inflammatory biomarkers) will be tested for significance using paired t-test or Wilcoxon test (for non-parametric data). A two-tailed alpha level of 0.05 will denote statistical significance.

miRNA analysis:

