The circulating miRNA-seq raw files in the FASTQ format will be subjected to adapted trimming, alignment, normalization, removal of low abundance miRNAs and analysis using the SMiRK pipeline.³⁷ The trimmed files will be aligned with mature miRNA sequences in the latest version of mirBase database with read counts as the output, which will be normalized by rpm (reads per million) method, between libraries. With auto-elimination of miRNAs with <10 rpm, SMiRK will perform analysis on normalized data by arranging miRNAs as unsupervised hierarchical clusters. A Wilcoxon test will be used to compare miRNA expression levels. Differentially expressed miRNAs (p<0.05) will be validated with RT-PCR and Megaplex Pools protocol (Applied Biosystems). miRWalk database will be used to validate target gene expression.

Fecal microbiome 16s analysis:

The raw 16s sequence data will be converted to taxonomic profiles by grouping 16s sequences into Operational Taxonomic Units (OTUs) based on sequence similarity using an previously described protocol^{38, 39} as well as by generating de-novo OTU generation using *usearch*, a de novo OTU-picking tool (v6.0.307; http://www.drive5.com/). ^{40, 41} We will use Basic Local Alignment Search Tool (BLAST) to analyze each OTU's representative sequence against the most recent release of the Greengenes 16S database. ⁴² The microbial diversity among the treatment and placebo groups will be quantified and compressed into a single scalar statistic as previously described. ⁴³ Relative abundance plots will be

generated in QIIME for visual comparison of microbial abundances at each taxonomic level.

D: Potential risks of study participation

D.1.1. Potential adverse effects of Acarbose: Acarbose has been used extensively to treat diabetes internationally and has an excellent safety profile. The most common side effects are gastrointestinal, including diarrhea, flatulence and abdominal pain that result from the fermentation of unabsorbed carbohydrates and resultant gas production. In general, GI side effects develop within the first few days of therapy, are mild to moderate in severity, and decrease over time. There have been rare postmarketing reports of ileus and pneumatosis cystoides intestinalis associated with alpha-glucosidase inihibitors and use is contraindicated in the setting of colonic ulceration, colonic obstruction and in individuals at high risk for colonic obstruction.

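### Serum miRNAs are called differentially expressed at p<0.05 with no stated multiplicity adjustment, so a non-empty list is likely even if acarbose does nothing

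*Combined protocol and SAP*

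**What the plan says.** All references are to the combined protocol and SAP.

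- **Scope of the screen (C.3.2, miRNA analysis).** The miRNAs come from sequencing, not from a chosen panel: "The trimmed files will be aligned with mature miRNA sequences in the latest version of mirBase database with read counts as the output". The only reduction before testing is an abundance filter: "With auto-elimination of miRNAs with <10 rpm, SMiRK will perform analysis on normalized data by arranging miRNAs as unsupervised hierarchical clusters".
- **Test and threshold (same place).** "A Wilcoxon test will be used to compare miRNA expression levels", and then "Differentially expressed miRNAs (p<0.05) will be validated with RT-PCR and Megaplex Pools protocol (Applied Biosystems". The plan states no adjustment, no fold-change condition and no count of miRNAs. It does not say whether the Wilcoxon test is the signed-rank or the rank-sum form.
- **Comparator (C.3.2, RNA-Seq).** Genes need an "adjusted p-value of less than 0.05" together with a fold change above 2.
- **Other outcomes (C.3.2, insulin sensitivity and biomarkers).** These use a "paired t-test or Wilcoxon test (for non-parametric data", at two-tailed 0.05.
- **Role (section B).** "As part of our secondary analyses, we also plan to assess changes in microRNA levels in the serum". A direction of interest is also stated: "We hypothesize that acarbose treatment will alter the expression of circulating miRNAs". C.3.2 describes the whole study as exploratory, with up to 30 men in a crossover.

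**The concern.** Two sequencing screens in one section are held to different standards, and no reason is given. The authors write the adjustment out for RNA-Seq, so a bare p<0.05 for miRNA reads most naturally as unadjusted.

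Section B hypothesises that acarbose alters circulating miRNAs. If the rule usually produces a list with no drug effect at all, the existence of that list says little about the hypothesis. The list also decides which miRNAs go to RT-PCR, and in the text the miRWalk target step follows directly. C.3.2 says data from this study will help design later interventions, so a list made up largely of chance findings could misdirect that work.

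**Working it through.** **Inputs.** From C.3.2: threshold 0.05 per miRNA, up to 30 pairs, crossover. Two-sided testing is stated for the biomarkers and assumed here for miRNA. The number of miRNAs tested, *m*, is not in the documents; I take 100 to 500 and show smaller values as well. The plan gives no error rate, power or effect size for this analysis, so it has no figure to reproduce.

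**Step 1: size of one test.** The exact two-sided signed-rank test at p<0.05 with 30 pairs has size 0.0497, so 0.05 is a fair working value.

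**Step 2: no drug effect, independent miRNAs.** Expected false calls = 0.05 × *m*. Chance of at least one = 1 − 0.95^*m*.

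| *m* | Expected false calls | Chance of at least one |
|---|---|---|
| 14 | 0.7 | 51% |
| 50 | 2.5 | 92.3% |
| 59 | 2.95 | 95.2% |
| 100 | 5 | 99.4% |
| 200 | 10 | >99.9% |
| 500 | 25 | >99.9% |

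A non-empty list is therefore more likely than not from 14 tests.

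**Step 3: correlated miRNAs.** I simulated 3,000 null trials per setting (30 pairs, normal paired differences, exact signed-rank test, one common correlation). With *m* = 200 the chance of any call was 1.00 at correlation 0, 0.993 at 0.3 and 0.81 at 0.6. At 0.6 it was 0.68 for *m* = 100 and 0.93 for *m* = 500. The mean number of calls stays near 10 for *m* = 200, but at 0.6 the median is 3: false calls arrive in clusters. At a common correlation of 0.8 the chance falls to about 31%, 37%, 45% and 48% for *m* = 50, 100, 200 and 300.

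**Step 4: some miRNAs truly respond.** Take *m* = 200, 30 pairs, independent miRNAs, and effects in units of the SD of the paired difference. Power at raw p<0.05 is 0.74 at 0.5 SD and 0.99 at 0.8 SD.

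- 10 true effects: false calls 190 × 0.05 = 9.5. True calls are 7.4 at 0.5 SD and 9.9 at 0.8 SD. False share is 9.5/16.9 = 0.56 and 9.5/19.4 = 0.49 (simulated means 0.55 and 0.48).
- 20 true effects: false calls 180 × 0.05 = 9. True calls are 14.8 and 19.8. False share is 9/23.8 = 0.38 and 9/28.8 = 0.31 (simulated means 0.38 and 0.31).

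**Step 5: the same data under Benjamini-Hochberg (BH) at 0.05.** With no effect, any call occurs in 0.050 of trials (independent) and 0.027 (correlation 0.6). Normal-approximation p-values give about 0.01 to 0.03. In the four settings of step 4 the false share is about 0.045.

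**Step 6: if the rank-sum form were used on paired data.** Per-test error falls to about 0.023, 0.0074 and 0.001 at within-man correlation 0.3, 0.5 and 0.7. With *m* = 200 that is 4.6, 1.5 and 0.2 false calls, and a chance of any call of about 98%, 79% and 21%. A repeat run gave 0.021 in place of 0.023. Power at 0.5 SD drops from 0.74 to 0.61 (correlation 0.3) or 0.19 (correlation 0.7).

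**Step 7: RT-PCR as a safeguard.** The plan names no independent samples. If the same serum is re-assayed with assay error equal to that of sequencing, 40% of null hits reach p<0.05 again when assay error is 20% of the variance of paired differences, and 17% when it is 50%. The assay-error shares are illustrative assumptions.

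**The case against.** The best defence is that this is a secondary screen in an exploratory study. No primary result depends on it, hits go on to a second assay, and a generous threshold is legitimate when missing a real signal is the main worry. That stands as a limit on severity. It does not justify the label: the plan also calls its RNA-Seq analyses exploratory, yet adjusts them, and a generous screen should be described as one.

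Second, *likely* depends on assumptions. It fails at a common correlation near 0.8, or if the rank-sum test is applied to strongly paired data. Both are true. The first is extreme. The second would be the wrong test for a crossover and would pay for fewer false calls with a large loss of power.

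Third, the cited pipeline may adjust its p-values. This cannot be checked from the documents, so the point is that no adjustment is stated, not that none would be done.

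Fourth, a list much longer than chance predicts, or one with very small p-values, would carry information. I accept that: the weakness lies in the p<0.05 label taken alone.

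Finally, the plan does not say that RT-PCR would reuse the same serum. Nor does it describe other samples, so it cannot be counted on to remove chance differences between a man's two periods.

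**Conclusion.** The concern holds. As written, the miRNA rule will probably yield a list labelled as differentially expressed whether or not acarbose has any effect. With 100 to 500 miRNAs and a paired test, 5 to 25 false calls are expected under no effect. With 200 miRNAs the chance of any call is above 99% at correlation up to 0.3 and about 81% at 0.6. If 5 to 10% of 200 independent miRNAs respond at 0.5 to 0.8 SD, about a third to a half of the list is false.

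These sizes rest on an assumed *m*, the signed-rank form and normal paired differences. The exact percentages would move with the real count and correlation; the conclusion needs only a modest number of tests. It should be fixed, but it affects a secondary analysis only. The RNA-Seq differential-expression rule for muscle and fat already uses adjusted p-values.

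**What to change.** In C.3.2, miRNA analysis: (1) name the paired signed-rank test for each miRNA passing the 10 rpm filter; (2) report how many were tested; (3) define differential expression as BH adjusted p<0.05, in line with the RNA-Seq rule; (4) if a wider net for RT-PCR is wanted, state a looser false discovery rate (FDR), for example below 0.20, and call those miRNAs candidates. If the pipeline already adjusts, one clause saying so settles item 3.

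The edit is one line of plan and one line of code, with no new samples. The real cost is power per miRNA (200 independent miRNAs, 10 true effects):

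| Pairs | Effect | Raw p<0.05 | BH 0.05 | FDR 0.20 |
|---|---|---|---|---|
| 30 | 0.5 SD | 0.74 | 0.16 | 0.40 |
| 30 | 0.8 SD | 0.99 | 0.81 | 0.94 |
| 20 | 0.5 SD | 0.54 | 0.04 | 0.16 |
| 20 | 0.8 SD | 0.91 | 0.41 | 0.71 |

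For moderate effects the loss is substantial, and the candidate list recovers only part of it. That is the reason to keep a labelled second tier rather than drop the wider screen.

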The mechanism by which acarbose delays aging in mice is not established. Some authors have hypothesized that acarbose acts as a "caloric restriction mimetic." Caloric restriction (CR) is known to extend lifespan in some model organisms and healthspan in human and non-human primates. Although acarbose does not substantially lower net caloric exposure, like CR, it decreases fasting insulin and weight, improves glucose metabolism, and in mice, mimics some of the metabolomic changes seen with CR.^{2,3,6} ¹² In humans, acarbose has postprandial effects that include a decrease in lipids^{13,14} and inflammatory mediators, ¹⁵⁻¹⁷ an increase in postprandial nitric oxide and nitric oxide synthase¹⁸, and an improvement in endothelial function, suggesting that acarbose protects from adverse consequences of a prandial nutrient load. ¹⁹ However, it is not known whether such changes may contribute to the anti-aging effects of acarbose.

Acarbose also alters gut microbiota²⁰ and increases serum butyrate,²¹ a fermentation byproduct that is associated with improved glucose metabolism. Gut microbes are increasingly recognized as important mediators of inflammatory and metabolic processes in humans. With age, there is a change in gut microbial species, and certain profiles have been associated with frailty.^{22, 23} So the question naturally arises as to whether human gut microbiota directly influence aging, and if acarbose might alter this process. Acarbose also increases circulating postprandial GLP-1 levels by up to 50% and alters the secretion of other gut hormones, which might also contribute to its beneficial effects.^{24, 25} Finally, it is possible that the absorbed metabolites of acarbose have direct effects on tissues.

In summary, acarbose improves lifespan and age-related memory loss in mice and represents one of the most promising anti-ageing compounds tested by the Interventions Testing Program. In humans, it decreases the risk of certain age-related diseases, including diabetes, cardiovascular disease and colorectal cancer. It is an inexpensive, FDA-approved medication that has been used safely for many years. We hypothesize that acarbose might extend healthy lifespan in humans. As an initial step to test this hypothesis, we plan to study changes in gene transcription and a variety of biomarkers in older adults at risk for cardiometabolic disease.

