Assessment of insulin sensitivity: Insulin sensitivity will be estimated from insulin and glucose levels obtained following the standard meal challenge, using a modification of the Matsuda index, which has been widely used for non-invasive assessment of insulin sensitivity and shows good correlation (r=0.73) with results obtained from euglycemic hyperinsulinemic clamp studies.³⁴

Measurement of markers of inflammation and oxidative stress: Measurement of circulating cytokines and acute phase reactants will be performed both fasting and at 2 hours postprandial. Plasma samples will be aliquoted into Eppendorff tubes and stored at -80° C. Subsequent measurements might include hormones, and inflammatory markers, including plasma leptin, TNF- α , PAI-1, IL-1 β , IL-6, VCAM, FGF-21, butyrate, alpha dicarbonyls, adiponectin and other aging biomarkers. Urine samples will be stored (in the presence of an antioxidant, such as BHA) and may be assayed for measurement of urine F2 isoprostanes.

Serum microRNA:

miRNA will be extracted from the serum samples using miRNeasy kit (Qiagen, CA) using the manufacturer's protocol. miRNA libraries will be prepared using NEBNext Multiplex Small RNA Library Prep for Illumina (New England Biolabs). Cel-miR-39 mimic will be added to each sample before extraction, for normalization and sent for miRNA sequencing at Einstein's Sequencing Core Facility using multiplexed single-end sequencing on an Illumina HiSeq2500

Fecal analysis for gut microbiome:

Stool collection and DNA extraction:

Stool samples will be collected at visits 4 and 6. 16s ribosomal DNA sequencing will be performed to assess bacterial species clustering. Participants will be provided with a DNA OMNIgene.Gut OMR200 kit (DNA Genotek, London, Canada) along with a stool collection hat, for self-collection of fecal samples, to be brought in for further treatment and analysis, at baseline visit 20f the study and after 12 weeks of study treatment on visit 4. The kits will be stored at room temperature until fecal microbial DNA extraction (within 30 days). Fecal microbial DNA will be extracted from the samples using PowerFecal DNA Isolation kit (MoBio Labs Inc) following manufacturer's protocol and eluted DNA will be divided into 1cc aliquots and frozen immediately at -80°C for further analysis. The purified DNA samples will be sent for 16s rDNA sequencing to Integrated Microbiome Resource, CGEB, Canada or at the Massachussets Institute of Technology (MIT).

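### The 16S plan states no test of composition or of any taxon, so a compositional shift under acarbose could be seen on plots but not established

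*Combined protocol and SAP*

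**What the plan says.** The 16S analysis plan is the short paragraph on the fecal microbiome at the end of section C.3.2. Reads become OTU-based taxonomic profiles by two routes, a previously described protocol and a de novo method. Then "The microbial diversity among the treatment and placebo groups will be quantified and compressed into a single scalar statistic", with the definition left to a cited reference. Finally, relative-abundance plots are "generated in QIIME for visual comparison of microbial abundances at each taxonomic level". The paragraph names no index, test, between-sample distance, taxon-level comparison or multiplicity control.

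Other sections say what the sequencing is for:
- Section B, on mechanism: "Acarbose also alters gut microbiota".
- Section B, closing paragraph: "Given the known effects of acarbose on colonic fermentation and composition of gut microbiota we plan to explore changes in gut microbiome". The same paragraph plans to correlate "post-translational regulation (miRNA) and gut microbiome with changes in clinical metabolic outcomes and inflammatory biomarkers", without saying which microbiome variable is meant.
- Section C.2.2, on fecal analysis: "16s ribosomal DNA sequencing will be performed to assess bacterial species clustering". No clustering method, distance or test follows.

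**The concern.** The stated rationale is a change in which bacteria are present and in what proportion. The only quantity that the plan commits to is a measure of diversity, which is a different property. Within-sample indices depend on the list of abundances and not on which taxon holds which. Two communities with different dominant bacteria can therefore have the same value.

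The remaining tool is visual. A shift might be visible on the plots, but the plan has no step that would say whether it exceeds chance or how large it is. Taxa singled out by eye across several taxonomic levels would carry no error control.

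The other sequencing assays in C.3.2 are treated differently: RNA-Seq has a count model with adjusted p-values, and miRNA has a Wilcoxon test. C.3.2 also says that the data will be used to estimate effect sizes for later studies. A diversity scalar supplies no compositional effect size.

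**Working it through.** The documents give no effect size, variance, power or test for the microbiome, so there is no planned figure to reproduce.

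**Inputs from C.3.2.** Up to 30 men in a crossover, giving 30 pairs. Two-sided alpha of 0.05, which the plan states for insulin sensitivity and inflammatory biomarkers and which is borrowed here. All other inputs are assumptions.

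**1. Exchange of two taxa (exact).** Take abundances (0.30, 0.10, 0.20, 0.15, 0.15, 0.10) and exchange the first two.
- Shannon, −Σ p ln p: 0.3612 + 0.2303 + 0.3219 + 2 × 0.2846 + 0.2303 ≈ 1.713. The terms are the same after the exchange, so the index stays at 1.713.
- Simpson, 1 − Σ p²: 1 − (0.09 + 0.01 + 0.04 + 0.0225 + 0.0225 + 0.01) = 0.805, before and after.
- Bray-Curtis, ½ Σ |p − q|: ½ (0.20 + 0.20) = 0.20.

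One fifth of the community has turned over and both indices are unchanged. No sample size alters that.

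**2. What a paired test on the scalar can detect.** For 80% power with 30 pairs, the normal approximation gives a standardised change of (1.960 + 0.842)/√30 = 0.51; the noncentral t gives 0.53. With 24 pairs the noncentral t gives about 0.60. These are changes in diversity, not in composition.

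**3. Illustrative power.** Assumed: 10 taxa, between-man SD 1.0 on the log scale, 20,000 reads per sample, and 300 to 500 replicates per reported run. Each run used its own assumed baseline profile, so the figures are good to a few percentage points. Ranges show separate runs.

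| Assumed change | Men | Within-man log SD | Paired test on Shannon | Paired per-taxon tests, Benjamini-Hochberg |
|---|---|---|---|---|
| Minor taxon doubled, major halved | 30 | 0.5 | 15–17% | about 100% |
| Major doubled, minor halved | 30 | 0.5 | 61–65% | 98–100% |
| Major tripled | 30 | 0.5 | 88–90% | 98–100% |
| Major doubled, three minors halved | 30 | 0.5 | about 92% | at least 98% |
| Minor doubled, major halved | 30 | 1.0 | about 8% | 68% |
| Minor doubled, major halved | 20 | 1.0 | about 8% | 43% |

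In the last two rows a paired permutation test of overall composition had power of 71% and 51%. With no effect, the paired methods rejected in 4 to 7% of trials.

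**4. A second design.** Assumed: 40 taxa, 10,000 reads, between-man SD 1.0, within-man SD 0.7, five taxa raised and five equally abundant taxa lowered by 0.5 log units (a factor of e^0.5 ≈ 1.65), 500 replicates. A Wilcoxon signed-rank test on Shannon rejected in 4% of trials, which is its null rate. A within-man sign-flip test on centred log-ratios rejected in 99.8%. At least one taxon was found after Benjamini-Hochberg adjustment in 97%.

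The direction of change drives the scalar's power. Raising a minor taxon while lowering a major one is close to an exchange, so the effects on evenness largely cancel. Raising a major taxon changes evenness, and the index responds.

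**The case against.** The strongest objection is that the index is defined only in a reference that the documents do not reproduce. The sentence speaks of diversity among groups and never says that each sample gets its own value. A between-group statistic would not be blind to an exchange of taxa. This stands, so the argument in step 1 is conditional on a within-sample index. It does not remove the gap, because no test is stated under either reading.

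A reader might infer several stronger points that the documents do not support:
- **That a real shift would go unnoticed.** Full taxonomic profiles are kept and plotted at every level, so a clear change could be seen. What is missing is a way to confirm and size it.
- **That the scalar will be tested unpaired.** The groups can simply be the two crossover conditions. No test is named, so no unpaired test is planned.
- **That Sub-aim 1 cannot be met.** Neither section B nor C.2.2 limits the microbiome variable to the scalar, and OTU profiles will exist for each sample.
- **That Shannon power is about 15%.** That is an unfavourable pattern. Other patterns give 60 to 90%.

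The microbiome is also one of several optional secondary domains in a study that calls itself exploratory. No primary conclusion, sample size or safety decision depends on it.

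**Conclusion.** The concern holds as a gap between the stated hypothesis and the stated analysis. The protocol expects a change in composition, and C.3.2 contains no inferential analysis of composition or of any taxon.

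On the assumption of a within-sample index, the scalar's ability to register a compositional change depends on the pattern of that change. Power is about 15% to about 90% across the assumed patterns at within-man SD 0.5, against about 98 to 100% for paired per-taxon tests. At within-man SD 1.0 the least favourable pattern gives about 8% against about 70%. None of these is a forecast for this trial. They show that composition-based tests on the same samples did at least as well in every pattern tried, and often far better.

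The weight is moderate: a cheap improvement to a secondary, exploratory analysis.

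**What to change.** Amend the microbiome paragraph of C.3.2 as follows, with all tests labelled exploratory:

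1. Name the diversity index and test it as a within-man acarbose-minus-placebo difference.
2. Add a paired multivariate test of composition, for example PERMANOVA on Bray-Curtis or Aitchison distance with permutations restricted within man.
3. Add paired per-genus tests on log-ratio-transformed abundances with Benjamini-Hochberg false-discovery control, reporting effect sizes with intervals.
4. Use the relative-abundance plots for display only.
5. State which of the two OTU tables is the basis for these analyses.

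Other methods of the same kind would also serve; what matters is that pairing, composition and multiplicity are dealt with in advance.

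The paired contrast also depends on the sampling times. C.2.2 gives stool collection at visits 4 and 6, but also at visit 2 and after 12 weeks of treatment at visit 4, while the schedule puts visit 4 at week 10. These statements need to be reconciled. C.3.1 recognises that gut microbial changes may outlast the 2-week washout, so period and possible carryover should be considered when the contrast is read.

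The cost is a change of wording, a few hours of analysis and more exploratory tests to report. No new samples are needed.
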